The Investigator should **assess** each SAE for the likelihood that it is a response to the investigational medicines. The SAE will also be evaluated by an allocated Clinical Reviewer at the request of UoSCTU for seriousness, expectedness and causality. Investigator reports of suspected SARs will be reviewed immediately and those that are SUSARs identified and reported to regulatory authorities. The causality assessment given by the Investigator cannot be overruled and in the case of disagreement, both opinions will be provided to the authorities with the report.

All SUSARs reported to UoSCTU will be forwarded to Merck kGaA.

13. Protocol deviations and withdrawal of patients

All protocol deviations should be reported to University of Southampton Clinical Trials Unit at the earliest opportunity.

In consenting to the trial, patients are consenting to trial treatment, trial follow-up and data collection. If a patient wishes to withdraw from trial treatment, centres should nevertheless explain the importance of remaining on trial follow-up, or failing this of allowing routine follow-up data to be used for trial purposes. If the patient explicitly states their wish not to contribute further data to the study, UoSCTU should be informed in writing and an End of Study form completed.

13.a Withdrawal from trial intervention

A patient may withdraw, or be withdrawn, from trial treatment for the following reasons:

- Progression whilst on therapy
- Unacceptable toxicity
- Intercurrent illness which prevents further treatment
- Withdrawal of consent for treatment by patient
- Any alterations in the patient's condition which justifies the discontinuation of treatment in the investigator's opinion.

The patient should however remain in the trial for the purposes of follow-up and data analysis.

14. Trial closure

We plan to recruit 288 patients which we anticipate we will reach at the end of December 2012. We will then follow-up all patients for 5 years after the trial closes to patient entry.

For the purposes of regulatory requirements the end of the trial will be the final date on which data was (or is expected to be) collected'.

15. Quality of life

15.a QoL timing

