18. Analysis plan and statistics

This 2 arm trial will compare the experimental arm (OxMdG-C/IrMdG-C, ARM B) against the control (OxMdG/IrMdG, ARM A).

Sample Size Calculation

The original EPOC trial (EORTC 40983) compared patients having surgery alone to patients being treated with pre and post operative chemotherapy with FOLFOX⁴². It assumed that chemotherapy may increase the median progression free survival by 40% from 16 months to 22.4 months. The power calculation study required 330 patients (165 in each arm) and 364 were actually recruited. The study demonstrated that peri-operative FOLFOX improved PFS and is compatible with major liver surgery⁴². This trial studied a group of patients with favourable liver metastases (4 lesions or less, mainly metachronous presentation). The group being studied in the current proposal has a considerably worse prognosis^{1-10, 46} as it includes patients with synchronous presentation and with sub optimal operability. An open study of such a group of patients treated with FOLFOX chemotherapy and surgery revealed a median progression free survival of around 17 months⁴⁷. The current proposal will also recruit a cohort of patients with metachronous disease who have received adjuvant Oxaliplatin. The survival of this group is less good than those patients treated with 5FU alone. However, metachronous disease patients suitable for FOLFOX have improved PFS compared to synchronous disease patients. Considering published data and the target patient population for this trial the expected median PFS for the control group is 15 months. The Crystal study⁴⁹ randomly assigned 599 patients with epidermal growth factor receptor-positive colorectal cancer with unresectable metastases to receive FOLFIRI either alone or in combination with Cetuximab. The results found the overall hazard ratio observed for progression free survival among 348 patients with wild-type-KRAS tumours was 0.68 (95% CI, 0.5 to 0.94). The results from the Crystal study have been used to power the New EPOC trial because it is internationally accepted as the best demonstration of Cetuximab in advanced colorectal cancer and if in New EPOC an effect less than this is observed it would be questionable as to whether it would be considered clinically meaningful. Further, bearing in mind the cost of antibody treatment, a hazard ratio greater than this would not justify its routine use. Using a hazard ratio of 0.68, assuming 80% power, a 5% 2-sided significance level and 5% loss to follow up by 2 years the total number of patients required with kRAS wild type genotype in the primary tumour is 268 (134 in each arm). This means the total sample size required for New EPOC is 288. This ensures the 20 patients for whom their kRAS status is unknown as they were recruited before the protocol amendment are replaced. The total sample size 268 patients with kRAS wild type genotype in the primary tumour is powered to detect 212 target events (disease progression). The sample size calculation was performed using ART version 1.07 in STATA and assumed recruitment would take place over 3 years with 5 years of follow up. Baseline survival probabilities from EPOC were also used in the calculation. This assumed progression free survival at 1 year, 2 years and 3 years was 67%, 46% and 35% respectively.

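### The sample-size paragraph expects a 15-month control median PFS but derives its 268 patients from a curve whose median is about 21 months

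*Protocol*

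**What the plan says.** The sample-size calculation in Section 18 (Analysis plan and statistics) describes EPOC as a trial in patients with favourable liver metastases and says of the present trial: "The group being studied in the current proposal has a considerably worse prognosis". It cites an open study of comparable patients with a median PFS of around 17 months, weighs the mix of synchronous and metachronous disease, and concludes that "the expected median PFS for the control group is 15 months".

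The design inputs follow: "Using a hazard ratio of 0.68, assuming 80% power, a 5% 2-sided significance level", and "5% loss to follow up by 2 years". The results are 268 kRAS wild-type patients, 134 per arm, and 212 target events, with recruitment over 3 years and 5 years of follow-up. Section 14 (Trial closure) repeats the follow-up period: "We will then follow-up all patients for 5 years after the trial closes to patient entry".

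The paragraph closes by saying that EPOC's baseline survival probabilities went into the calculation: "This assumed progression free survival at 1 year, 2 years and 3 years was 67%, 46% and 35% respectively". No baseline figure beyond year 3 is given.

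**The concern.** The paragraph justifies one control-arm assumption at some length and then calculates with another. The assumption it uses comes from the trial whose population it has just described as having the better prognosis.

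In a time-to-event design the number of events follows from the hazard ratio, alpha and power alone. The control curve determines how many patients, and how much follow-up, are needed to reach that number. Two control curves therefore give two values of N or two event timelines. A data monitoring committee that is to set the frequency of its reviews by accrual and event rates (Section 24) would have two benchmarks for the same trial. A reader who tries to rebuild 268 from the 15-month figure will not succeed.

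**Working it through.** **Inputs, all from Section 18:** HR 0.68; two-sided 5%; 80% power; 1:1 allocation; 3 years' recruitment, taken as uniform; 5 years' further follow-up; 5% loss by 2 years, which as a constant hazard is −ln(0.95)/2 = 0.0256 per year; control PFS of 67/46/35%; stated control median of 15 months.

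**1. Events (the plan's own figure).** Schoenfeld: d = 4 × (1.960 + 0.842)² / (ln 0.68)² = 211.1, so 212. Power at 212 events is 80.2%. The plan's figure is reproduced, and no median enters the formula.

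**2. Median of the curve used.** Piecewise-exponential hazards through the three points are −ln(0.67) = 0.400, −ln(0.46/0.67) = 0.376 and −ln(0.35/0.46) = 0.273 per year. PFS reaches 50% in the second year, at 12 + 12 × ln(0.67/0.50)/0.376 = 21.3 months. Linear interpolation gives 21.7 months. The exponential medians implied by each point alone are 20.8, 21.4 and 23.8 months.

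**3. Curve implied by 15 months.** An exponential curve with S(t) = 0.5^(t/1.25), t in years, gives 57%, 33% and 19% at 1, 2 and 3 years. For a 15-month median to fit the stated points, PFS would have to fall from 67% to 50% in 3 months and then only to 46% over the next 9. Nothing in the text suggests such a shape.

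**4. Which assumption gives 268?** The event probability was averaged over uniform entry (5 to 8 years of follow-up) and over the two arms, with proportional hazards at 0.68. Two things are not stated and were varied: the hazard after year 3 and the way the 5% loss is applied.

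| Control assumption | Loss | Events from 268 | N for 212 events | Years from recruitment close to event 212 (N = 268) |
|---|---|---|---|---|
| EPOC curve, average 0–3 year hazard (0.350) continued | constant | 212.4 | 268 | 5.0 |
| same | to 2 years only | 216.8 | 263 | 4.6 |
| same | none | 224.4 | 254 | 4.1 |
| EPOC curve, year-3 hazard (0.273) continued | constant | 203.7 | 279 | 5.9 |
| same | to 2 years only | 207.6 | 274 | 5.4 |
| same | none | 214.8 | 265 | 4.8 |
| Exponential, median 15 months | constant | 240.5 | 237 | 2.5 |
| same | none | 251.7 | 226 | 2.1 |

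The first row reproduces the plan's 268 and 212 at its own 5 years. The 15-month rows need 226 to 237 patients for 212 events, or about 225 if the unrounded 211.1 events is used (211.1/0.939). With 268 patients their power is 84.9% at 240 events and 86.4% at 252. A 15-month exponential gives N = 268 only if follow-up is cut to about 2.5 years, which neither Section 14 nor Section 18 says.

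**The case against.** The strongest reply is that the calculated design is coherent. Hazard ratio, alpha, power, 212 events, 268 patients, the EPOC curve and 3 + 5 years all fit together, and the 15-month sentence is the only outlier. The mismatch is also conservative: if 15 months is right, 268 is more than enough and the events arrive sooner. All of this stands. It limits the consequence but does not remove the contradiction. Because the Protocol itself states both figures, a separate analysis plan cannot cure it.

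Three stronger readings are tempting, and the documents do not support them.

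- *The trial is underpowered.* Power depends on events and the hazard ratio, and 212 events give 80%. A shortfall appears only if one supposes that PFS flattens after year 3. The Protocol states no such plateau, and the conflict between the two medians does not imply one.
- *The event timeline cannot be known.* On the curve actually used, event 212 falls about 4 to 6 years after recruitment closes, which agrees with the stated 5 years of follow-up.
- *An observed hazard ratio above 0.68 counts as failure.* The text says that "if in New EPOC an effect less than this is observed it would be questionable as to whether it would be considered clinically meaningful". This is a softly worded reason for choosing the target effect, with no success rule attached. The analysis plan in Section 18 reports the hazard ratio with its 95% confidence interval. That the estimate reaches the target only half the time when the target is true holds for any trial powered at its target effect.

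The date of the primary analysis may properly be left to the statistical analysis plan and is no part of this point.

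**Conclusion.** The point holds as an inconsistency in a sample-size input. The stated 15-month control median is not the assumption behind N = 268; the EPOC curve, with a median of about 21 months, is. The 212 events and the 80% power are right.

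The size of the discrepancy is about 30 to 40 patients (268 against 225 to 237), or equivalently about 5 percentage points of power in the favourable direction (85 to 86% against 80%). Event 212 would come roughly 2 to 4 years earlier than on the curve used.

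The 15-month figures assume an exponential curve; rescaling the EPOC shape to a 15-month median gives about 239 to 250 patients, still short of 268. The EPOC-curve range rests on an assumed hazard after year 3 and on how the 5% loss is applied, neither of which the Protocol states.

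**What to change.** Keep one control assumption in Section 18 and restate N, power and expected event timing from it. Either of these would do:

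- keep 15 months, replace the 67/46/35% figures with the matching curve, and give either its N (about 225 to 237 if exponential) or the power of roughly 85% at 268, with 212 events expected about 2 to 2.5 years after recruitment closes; or
- replace 15 months with the median of about 21 months actually used, explain why EPOC's curve suits a population described as having a worse prognosis, and state the hazard assumed after year 3 and how the 5% loss was applied, with the event timing that follows.

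The cost is a rewording of one paragraph. The target effect, the 212 events and the method of analysis stay as they are, and no extra patients are needed. Section 14 anticipated the end of recruitment in December 2012, so the purpose is a correct record of the design rather than a new recruitment target.

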- Patients will be randomised to the control or experimental arm by telephone to the MRC Clinical Trials Unit. Randomisation will utilise minimisation and the stratification factors are surgical centre, poor prognostic tumour (yes or no) and prior treatment with Oxaliplatin as adjuvant (yes vs. no). A poor prognostic tumour is defined as having any one or more of the following ≥ 4 metastases (yes or no), N2 disease (yes or no) or poor differentiation at biopsy (if available, if not available the tumour is considered to be not poorly differentiated).
- Complete the first page of the Baseline and Randomisation Form and telephone the MRC CTU on **[name]** (9am – 5pm, Mon-Fri).
- Details will be taken and the patient will be allocated a treatment and trial number. At that point, complete the remainder of the Randomisation Form and fax it to UoSCTU on **[name]**, together with the baseline QoL form and a copy of the signed Consent Form.
- Also at this point, provided the patient has not withheld consent for the translational studies:
 1. Ensure that the patient's pathology details are recorded on the **Randomisation and pre-treatment Form and request the pathology block from the relevant local pathology laboratory using the pathology request form.**
 2. Request stored pathology samples (normal and tumour tissue) from previous resection surgery of the patients' primary colorectal cancer and take 20 ml blood in an EDTA tube (2 tubes required if 10 ml size). Label each sample with the **date of collection and patient details**. Seal the tube(s) in a plastic bag, place in a Royal Mail 'safeBox' provided by UoSCTU and post first-class with a copy of the patient consent form and any histology information available. The address for posting is:

New EPOC Trial Sample laboratory
Cancer Sciences Tissue Bank
[name]
[name]
[name]
[name]

11.d Start of chemotherapy

Treatment should start as soon as possible after randomisation. However, a delay of up to 3 weeks from randomisation to start of treatment (e.g. for venous line insertion) may elapse if clinically acceptable. Patients should still be treated within 4-6 weeks of the cross sectional imaging scan used to assess their disease. If the patient will receive infused 5FU in OxMdG or IrMdG but the line cannot be fitted sufficiently quickly, give the first cycle of treatment as an inpatient.

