
Initial analysis plan

The primary outcome measure is progression free survival. The two treatment groups will be compared on an intention to treat basis. Comparison of survival between the two treatment groups will be performed using Cox regression. The hazard ratio and 95% confidence interval will be reported. The primary analysis will be unadjusted and will include only patients whose primary tumour has been confirmed as kRAS wild type genotype. Sensitivity analyses may be adjusted for any confounding variables if, by chance, there are imbalances between the groups. The primary analysis will be repeated including only patients whose primary tumour has been confirmed as kRAS wild type genotype and who were not treated with CAPOX. The DMEC will also regularly review the trial data. Serial analyses will not be performed, except by the DMEC.

There will also be a planned combined analysis with arms A and B of the COIN study to evaluate the intention to treat effect of Cetuximab on all patients with advanced disease. In this combined analysis consideration for confirmed kRAS status in the primary tumour will be made. Comparison of survival between the two treatment groups will be performed using Cox regression, adjusted for stratification factors. The hazard ratio and 95% confidence interval will be reported. The analyses will be adjusted for any confounding variables if, by chance, there are imbalances between the groups. The DMEC will also regularly review the trial data.

19. Patient confidentiality

The University of Southampton is registered under the Data Protection Act to hold data as required for trial purposes. Patients will be allocated a unique trial number that will be used in all correspondence with the participating centres. At no point in the presentation or publication of trial data will individual patients be identified. Each patient's GP will be notified of their enrolment in this clinical trial using the associated GP letter (if consent is provided).

20. Monitoring and quality assurance

20.a Monitoring at UoSCTU

The study will be monitored and audited in accordance with University Hospital Southampton NHS Foundation Trust (UHS) procedures. All trial related documents will be made available on request for monitoring and audit by UHS, the relevant REC and for inspection by the MHRA or other licensing body.

20.b Direct access to data

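### The primary PFS Cox model omits the prognostic factors used in minimisation: the test is valid but conservative, and it forgoes some efficiency

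*Protocol*

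**What the plan says.** Allocation is described in Protocol section 11.c: "Randomisation will utilise minimisation and the stratification factors are surgical centre, poor prognostic tumour (yes or no) and prior treatment with Oxaliplatin as adjuvant". The same section builds the tumour factor from adverse features: "A poor prognostic tumour is defined as having any one or more of the following", namely four or more metastases, N2 disease or poor differentiation. Section 18 (Sample Size Calculation) adds that patients who relapse after adjuvant oxaliplatin survive less well than those given 5FU alone.

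Section 18 (Initial analysis plan) sets the method for PFS: "Comparison of survival between the two treatment groups will be performed using Cox regression". It then fixes the covariates: "The primary analysis will be unadjusted and will include only patients" with a confirmed kRAS wild-type primary tumour. Covariates appear only in an optional second step: "Sensitivity analyses may be adjusted for any confounding variables if, by chance, there are imbalances between the groups".

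The next paragraph, on the combined analysis with COIN, makes a different choice. That comparison is to be "performed using Cox regression, adjusted for stratification factors".

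Section 26 records that the stratification factors were updated on 16 January 2008 and again on 22 April 2009.

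**The concern.** Minimisation forces the arms to be similar on factors that predict PFS. The difference between arms then varies less from trial to trial than under simple randomisation, but an unadjusted Cox model does not know this. Its standard error is too large relative to the true sampling variation, so the test rejects less often than its nominal level. Omitting a prognostic covariate from a Cox model also moves the estimated hazard ratio towards 1 compared with the covariate-specific (conditional) one. Both effects cost power.

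The fallback does not repair this. It brings in covariates only when an imbalance is seen, and minimised factors are the least likely to be imbalanced. The covariates that most belong in the model are therefore the ones the rule is least likely to select.

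At stake is some power in a trial designed at 80%, and clarity about which hazard ratio is compared with 0.68. Section 18 treats 0.68 as the limit above which routine use would not be justified.

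**Working it through.** **Inputs from the protocol (section 18).** Hazard ratio 0.68, 80% power, two-sided 5%, 268 kRAS wild-type patients (134 per arm), 212 events, expected control median PFS 15 months.

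**The plan's own figure.** Schoenfeld's formula for 1:1 allocation is events = 4(1.960 + 0.842)² / (ln 0.68)² = 31.40 / 0.1487 = 211.1, rounded up to 212. Power at 212 events: 0.3857 × √212 / 2 − 1.960 = 0.848, which corresponds to 80.2%. The design figure reproduces.

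**Assumptions not in the protocol.** 40% poor prognostic tumour; 15% prior adjuvant oxaliplatin; 20 centres; minimisation with an 80% biased coin on centre and the two binary factors; no centre effect unless stated; all patients minimised on the current factors. There were 4,000 replicates per scenario, analysed at 212 events. The unadjusted Cox model was compared with one adjusted for the two binary factors. In this table 0.68 is the conditional hazard ratio.

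| Factor HRs (poor prognosis / prior oxaliplatin) | Null model SE vs true SD, unadjusted | Type I error, unadjusted vs adjusted | Mean estimated HR, unadjusted vs adjusted | Power, unadjusted vs adjusted |
|---|---|---|---|---|
| 1.0 / 1.0 | 0.1379 vs 0.1394 | 5.1% vs 5.4% | 0.677 vs 0.675 | 80.3% vs 80.5% |
| 1.3 / 1.2 | 0.1379 vs 0.1378 | 4.7% vs 5.1% | 0.680 vs 0.675 | 79.1% vs 80.1% |
| 1.5 / 1.3 | 0.1379 vs 0.1365 | 4.8% vs 5.2% | 0.685 vs 0.675 | 78.2% vs 80.2% |
| 2.0 / 1.5 | 0.1379 vs 0.1322 | 4.2% vs 5.3% | 0.698 vs 0.676 | 75.2% vs 80.4% |
| 2.5 / 2.0 | 0.1378 vs 0.1279 | 3.5% vs 5.3% | 0.713 vs 0.676 | 70.1% vs 80.2% |

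In the last four rows the unadjusted SE is too wide by about 0%, 1%, 4% and 8% (for example 0.1379 / 0.1322 = 1.04). The power differences are about 1, 2, 5 and 10 points. The Monte Carlo SE of a 5% rejection rate is √(0.05 × 0.95 / 4000) = 0.34 points, so 4.7% and 4.8% cannot be told from 5%; 4.2% and 3.5% can.

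**A second simulation** compared log-rank with stratified log-rank, with allocation balanced within strata and 20% prior oxaliplatin at HR 1.3. Power was 78% vs 79% at a poor-prognosis HR of 1.5, 75% vs 79% at 2.0, and 71% vs 78% at 2.5.

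**If 0.68 is marginal.** The conditional HR was reset so that the unadjusted estimate averages about 0.68 (conditional 0.671 and 0.658; mean unadjusted estimate 0.676 in both). Power is then 81.0% unadjusted vs 82.7% adjusted at 1.5 / 1.3, and 82.1% vs 86.5% at 2.0 / 1.5.

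**With a centre effect** (SD 0.3 on the log hazard) added to the 1.5 / 1.3 scenario and a conditional HR of 0.68, power is 75.4% unadjusted vs 77.3% adjusted for the two factors only.

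The reported Cox SE barely changes with adjustment (about 0.138 to 0.140 in both models). The gain comes from removing the attenuation, and the size of the test returns to about 5%.

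**The case against.** The best defence is that an unadjusted, pre-specified primary model is legitimate. It leaves no covariate choice open, gives a marginal hazard ratio that many readers want, and does not inflate type I error. All of that stands, and it bars several stronger readings.

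- A reader might infer that the 5% level is not kept. The error is on the safe side (3.5% to 4.8% in the scenarios with prognostic factors), so the test is valid.
- A reader might infer that the trial really has 70% to 75% power. Those figures need strong factor effects and also treat 0.68 as conditional. Section 18 takes 0.68 as the overall hazard ratio observed in CRYSTAL and does not describe it as covariate-adjusted. Read as marginal, it leaves the unadjusted analysis with at least its 80%.
- A reader might call the shift towards 1 a bias. It reflects non-collapsibility: marginal and conditional hazard ratios are different quantities, and choosing the marginal one has some merit.
- A reader might see a contradiction with the COIN analysis. That analysis pools two trials, so a different model is not an error. It shows only that the investigators accept the principle elsewhere.
- A reader might see the imbalance rule as a threat to the primary result. It governs only optional sensitivity analyses.
- A reader might want the chemotherapy backbone added too. It is not an allocation factor and it overlaps with prior oxaliplatin, so this argument does not call for it.

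Two further limits apply. Unavailable differentiation is coded as not poor (section 11.c), which may dilute the tumour factor. And because the factors were changed during recruitment (section 26), the uniform balance simulated here is not established for earlier patients.

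The objection does not remove the main point. The protocol states the unadjusted rule outright, so this is not detail left to an analysis plan, and the rule ignores information that the design already uses.

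**Conclusion.** The point holds as one of efficiency. The unadjusted primary test is valid but conservative, and it gives up about 1 to 2 power points if the minimised factors are weakly prognostic (hazard ratio up to about 1.5). The loss is about 4 to 5 points or more at 2 or above, and nil if they are not prognostic. The protocol gives neither prevalences nor factor effects, so it cannot be said where in that range the trial lies. The gap persists when 0.68 is read as marginal (about 2 points at 1.5 / 1.3 and 4 at 2.0 / 1.5). In that case it is forgone efficiency above the planned 80%, not a shortfall below it.

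**What to change.** In section 18, make the primary PFS analysis a Cox model stratified by, or adjusted for, poor prognostic tumour and prior adjuvant oxaliplatin, using baseline values. Add:

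- a coding rule for both factors in patients randomised before the updates of January 2008 and April 2009;
- a pre-specified approach to surgical centre that suits small centres, for example a random effect or a sensitivity analysis;
- the unadjusted hazard ratio as a named sensitivity analysis;
- a statement that the allocation factors enter by design and not because an imbalance was observed.

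The cost is mainly wording, with no extra patients or visits. The current factors are recorded for allocation; for earlier patients, availability of the baseline values needs checking. The one real downside is that the headline hazard ratio becomes conditional and, with prognostic factors, will tend to lie further from 1 than the marginal one. The text should say so, and say which of the two is compared with the 0.68 threshold.
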